- The volume of distribution at steady-state (V_{ss})
- Mean residence time (MRT)
- Total body clearance (CL)
- Terminal half-life ($t_{1/2}$)

Statistical Methods:

Sample size

To calculate the approximate power for this study, it is assumed that the number of SBIs experienced per subject per year follows a negative binomial distribution with mean μ and variance $\sigma^2 = \mu(1+\phi\mu)$ where ϕ represents an overdispersion parameter reflecting possible inter-subject variability in the rates of SBIs between subjects. To demonstrate efficacy, it is required that the observed mean number of SBIs across the study population should have an upper 99% one-sided confidence limit below 1 infection per subject per year. This is equivalent to testing the one-sided null hypothesis, $H_0: \mu \geq 1$, against the alternative hypothesis, $H_0: \mu < 1$, where μ is the population mean rate of SBI's per subject per year.

Based on the mean and variance of the negative binomial distribution, standard one-sample power calculations for comparison of an observed mean with a theoretical alternative hypothesis indicate that for a study with 40 subjects (Cohort 1), the probability of the upper one-sided 99% confidence limit being less than 1 remains above 80% ($power \geq 0.798$) for overdispersion ranging from $\phi=0$ (corresponding to a Poisson distribution with no overdispersion) to $\phi=2$ provided that the true mean number of SBIs per subject per year in the population lies below 0.50. For a sample of 20 subjects (Cohort 2), this probability remains at or above 80% ($power \geq 0.798$) for overdispersion ranging from $\phi=0$ to $\phi=2$ provided that the true mean

number of SBIs per subject per year in the population lies below 0.40 (or 0.50 in the case when there is no overdispersion).

For practical purposes, the study should be considered adequately powered to demonstrate efficacy for a population in which the true incidence of serious acute bacterial infections is below 0.50 per subject per year.

General statistical approach

Analyses will be presented for the adult cohort (Cohort 1) and the pediatric cohort (Cohort 2) regardless of Study Group both separately and combined.

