12.1 Analysis Populations

The safety analysis set will consist of all subjects who are enrolled into the study and received study product. The all treated population analysis set will be the same as the safety set. A modified per-protocol population analysis set will be defined as all subjects in the full all treated population set who remain in the study for at least 6 infusions.

A per-protocol (PP) analysis set will consist of all subjects in the all treated population set who complete the whole 12-month study period and who do not have any major protocol violations as described in the Data Handling Plan.

The analyses described below will be presented for all subjects in the all treated population, the modified PP population, and the PP population as follows:

- Cohort 1 only;
- Cohort 2 only;
- Each of the 3 age groups within Cohort 2;
- Cohorts 1 and 2 pooled.

The primary efficacy analysis will be based on the all treated population analysis set, with separate analyses for Cohort 1 and Cohort 2.

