12.3.2 Primary Efficacy Endpoint

The primary efficacy endpoint in this clinical study is the rate of acute serious bacterial infections (pneumonia, bacteremia and septicemia, osteomyelitis/septic arthritis, bacterial meningitis, visceral abscess) per subject during the 12-month study observation period while receiving IMP. Serious bacterial infections (SBIs) must be confirmed with the tests and outcomes as described in Section 21.1.

The rate of occurrence of such infections will be calculated for each subject as $52n/w$ where n is the number of reported infections and w is the number of weeks on study.

For the primary endpoint, a 99% one-sided (upper) confidence limit for the incidence rate of SBIs (scaled to represent 12 months exposure if necessary) will be derived, and the objective of demonstrating that the true infection rate is below 1 per subject per year will be considered established if this upper limit is less than 1.

To calculate the confidence limit, a negative binomial regression model will be used. This model includes an over-dispersion parameter to account for possible intra-subject correlation as well as the actual time period each subject is on the study as an offset variable. The null hypothesis for this analysis is that the true SBI rate is at least 1 per subject per year, and the alternative hypothesis is that this rate is less than 1 per subject per year. Rejection of the null hypothesis is therefore equivalent to demonstration of the study objective to show that the true rate is less than 1 per subject per year.

The proposed method of analysis makes appropriate allowance for any intra-subject correlation in the incidence of SBIs. Such correlation would occur whenever variability in the individual subject-specific SBI rates exceeds what would be expected in the presence of true Poisson variability. The proposed statistical test based on a negative binomial model includes an overdispersion parameter reflecting any such inflated variance.

No formal statistical analyses will be done comparing the primary efficacy endpoint between the Waiting Period and the IMP Treatment Period.

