12.4 Sample Size

The power of this study to establish that the true infection rate is less than 1 per subject per year depends primarily on the unknown true infection rate. However, on the assumption that the number of serious bacterial infections (SBIs) per year follows a negative binomial distribution with mean μ and variance $\sigma^2 = \mu(1+\phi\mu)$ where μ is the population mean infection rate per year and ϕ is an overdispersion parameter reflecting possible variability in individual subject-specific rates, an estimate of the power can be made for a range of assumptions about the true infection rate.

The following table shows the estimated power of a study with 40 subjects (Cohort 1) or 20 subjects (Cohort 2) to achieve an upper 99% confidence limit below 1, for various true values of the population mean infection rate assuming a range of overdispersion from $\phi=0$ (corresponding to a Poisson distribution with no overdispersion) to $\phi=2.0$. These results were obtained using standard one-sample power calculations for testing the one-sided null hypothesis, $H_0: \mu \geq 1$, against the alternative hypothesis, $H_1: \mu < 1$, where μ is the population mean number of SBI's per subject per year. Specifically, the estimated power is given by $\text{Power} = 1 - \beta = \Pr[m + Z_{1-\alpha}\sigma < 1 | H_1]$ where m is the sample mean rate of infection, $Z_{1-\alpha} = 2.326$ is the standard normal quantile for an upper 99% confidence limit,

and $\sigma^2 = \mu(1+\phi\mu)$ is the true variance under the alternative hypothesis H_1 for some specified value μ that is less than 1.

Table 5. Calculations on Statistical Power

True population infection rate per subject per year and possible overdispersion		Chance of upper 99% one-sided confidence limit being below 1	
SBI rate μ	Overdispersion parameter ϕ	N=40 (Cohort 1)	N=20 (Cohort 2)
0.40	0 (Poisson)	99.9%	97.2%
	2.0	98.4%	79.8%
0.45	0 (Poisson)	99.8%	91.0%
	2.0	92.4%	63.1%
0.50	0 (Poisson)	98.4%	79.8%
	2.0	79.8%	46.4%
0.55	0 (Poisson)	93.5%	65.1%
	2.0	62.6%	32.5%
0.60	0 (Poisson)	82.6%	49.3%
	2.0	45.0%	22.1%

The study therefore has adequate power (80% or greater when rounded) provided that the true rate of serious bacterial infections in the study population is 0.50 per subject per year or below for adults, or 0.40 per subject per year or below for children, and if the assumption of a negative binomial distribution (or Poisson distribution when $\phi=0$) is appropriate.

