4. DETERMINATION OF SAMPLE SIZE

The power of this study to establish that the true infection rate is less than 1 per subject per year depends primarily on the unknown true infection rate. However, on the assumption that the number of SBIs per year follows a negative binomial distribution with mean μ and variance $\sigma^2 = \mu(1+\phi\mu)$ where μ is the population mean infection rate per year and ϕ is an overdispersion parameter reflecting possible variability in individual subject-specific rates, an estimate of the power can be made for a range of assumptions about the true infection rate.

The following table shows the estimated power of a study with 40 subjects (Cohort 1) or 20 subjects (Cohort 2) to achieve an upper 99% confidence limit below 1, for various true values of the population mean infection rate assuming a range of overdispersion from $\phi=0$ (corresponding to a Poisson distribution with no overdispersion) to $\phi=2.0$. These results were obtained using standard one-sample power calculations for testing the one-sided null hypothesis, $H_0: \mu \geq 1$, against the alternative hypothesis, $H_1: \mu < 1$, where μ is the population mean number of SBI's per subject per year. Specifically, the estimated power is given by $\text{Power} = 1 - \beta = \Pr[m + Z_{1-\alpha}\sigma < 1 | H_1]$ where m is the sample mean rate of infection, $Z_{1-\alpha} = 2.326$ is the standard normal quantile for an upper 99% confidence limit, and $\sigma^2 = \mu(1+\phi\mu)$ is the true variance under the alternative hypothesis H_1 for some specified value μ that is less than 1.

Table 1. Calculations on Statistical Power

True population infection rate per subject per year and possible overdispersion		Chance of upper 99% one-sided confidence limit being below 1	
SBI rate μ	Overdispersion parameter ϕ	N=40 (Cohort 1)	N=20 (Cohort 2)
0.40	0 (Poisson)	99.9%	97.2%
	2.0	98.4%	79.8%
0.45	0 (Poisson)	99.8%	91.0%
	2.0	92.4%	63.1%
0.50	0 (Poisson)	98.4%	79.8%
	2.0	79.8%	46.4%
0.55	0 (Poisson)	93.5%	65.1%
	2.0	62.6%	32.5%
0.60	0 (Poisson)	82.6%	49.3%
	2.0	45.0%	22.1%

The study therefore has adequate power (80% or greater when rounded) provided that the true rate of SBIs in the study population is 0.50 per subject per year or below for adults, or 0.40 per subject per year or below for children, and if the assumption of a negative binomial distribution (or Poisson distribution when $\phi=0$) is appropriate.

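### The synopsis's closing claim of adequate power below 0.50 SBIs per year does not hold for Cohort 2, for which the protocol's own Table 5 gives 46.4% to 79.8% at 0.50

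*Protocol*

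**What the plan says.** The success criterion is that the observed rate "should have an upper 99% one-sided confidence limit below 1 infection per subject per year" (Protocol Synopsis, Sample size). The null hypothesis is that "the true SBI rate is at least 1 per subject per year" (Protocol 12.3.2). The primary efficacy analysis uses the all treated set "with separate analyses for Cohort 1 and Cohort 2" (Protocol 12.1); SAP 6.1 and 10.1 say the same.

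The plan describes power in three places:

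- **Synopsis, Sample size.** For 40 adults, power "remains above 80" per cent (printed beside a figure of 0.798) for phi from 0 to 2 if the true rate is below 0.50. For 20 children, 0.798 or more over the same range of phi if the true rate is below 0.40, or below 0.50 when there is no overdispersion. The section then closes by saying that the trial "should be considered adequately powered to demonstrate efficacy for a population in which the true incidence of serious acute bacterial infections is below 0.50" (SBIs per subject-year). This last sentence names no cohort and no value of phi.
- **Protocol 12.4 with Table 5.** Power for N = 40 and N = 20 at rates from 0.40 to 0.60, with phi = 0 and phi = 2. The conclusion is 0.50 or below for adults and 0.40 or below for children, with 80% understood after rounding.
- **SAP 4 with Table 1.** The same table and the same conclusion.

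Protocol 12.4 and SAP 4 print the same formula: Power = Pr[m + Z·sigma < 1 | H1]. Here m "is the sample mean rate of infection", Z = 2.326 "is the standard normal quantile for an upper 99% confidence limit", and sigma² = mu(1 + phi·mu) "is the true variance under the alternative hypothesis". N does not appear.

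**The concern.** A closing sentence that speaks for the whole study is the one most likely to be carried into other documents. As worded, it gives both primary analyses a property that only the adult one has. Someone relying on it could read a failed Cohort 2 result, at a true rate of 0.45 to 0.50, as evidence against the product. With strong overdispersion, the protocol's own table puts the chance of success there between about an even bet and 63%.

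The formula raises a second, smaller question. A table that differs between N = 40 and N = 20 cannot come from an expression without N, so a reader who checks the table against the text cannot reproduce it.

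**Working it through.** **Inputs.** Null rate 1 (Protocol 12.3.2); Z = 2.326, N = 40 and 20, sigma² = mu(1 + phi·mu), phi = 0 to 2 (Protocol 12.4, SAP 4).

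**Step 1: reproduce Table 5.** With the standard error of the mean in place of sigma,

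Power = Phi( (1 − mu)·sqrt(N)/sigma − 2.326 ).

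| Cohort | mu | phi | sigma | (1 − mu)·sqrt(N)/sigma | Power | Table 5 |
|---|---|---|---|---|---|---|
| 1 (N = 40) | 0.50 | 0 | 0.7071 | 4.472 | 98.4% | 98.4% |
| 1 (N = 40) | 0.50 | 2 | 1.0000 | 3.162 | 79.8% | 79.8% |
| 2 (N = 20) | 0.40 | 2 | 0.8485 | 3.162 | 79.8% | 79.8% |
| 2 (N = 20) | 0.45 | 2 | 0.9247 | 2.660 | 63.1% | 63.1% |
| 2 (N = 20) | 0.50 | 0 | 0.7071 | 3.162 | 79.8% | 79.8% |
| 2 (N = 20) | 0.50 | 2 | 1.0000 | 2.236 | 46.4% | 46.4% |

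All 20 cells of Table 5 agree within 0.1 percentage point. The table was therefore computed with sigma/sqrt(N).

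**Step 2: test the closing sentence.** For Cohort 2 at 0.50, power is 79.8% at phi = 0, 60.1% at phi = 1 and 46.4% at phi = 2. Just inside the claimed range, at 0.499 with phi = 2, it is 46.7%. The highest true rate giving 80% with N = 20 is 0.499 at phi = 0 and 0.3995 at phi = 2. For N = 40 at phi = 2 it is 0.4995. The limits of 0.50 for adults and 0.40 for children therefore fit the table over the full range of phi; a single limit of 0.50 does not.

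Two possible rescues fail:

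- If all 25 planned children gave a full year of data, power at 0.50 with phi = 2 would be about 57%.
- Pooling to N = 60 gives 93.9%, but the pooled analysis is not the primary one.

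**Step 3: the formula as printed.** The smallest sigma in the table is sqrt(0.40) = 0.632, so Z·sigma is at least 2.326 × 0.632 = 1.47. The condition m + Z·sigma < 1 would then need a negative sample mean in every row, and power would be essentially 0%. If sigma is also read as the standard deviation of m, power is Phi((1 − mu)/sigma − 2.326). That is at most 8.4% (mu = 0.40, phi = 0) and 3.4% at mu = 0.50, phi = 2. Neither reading gives the table.

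**Step 4: scale of the planned limit.** Table 5 treats the limit as symmetric on the mean scale. Protocol 12.3.2 plans a negative binomial regression, and the SAP 10.1 code has a log link, with a Poisson distribution and deviance scaling. Two simulations were run, with one full year per subject, a log-scale 99% upper limit, and samples with no events counted as successes. Power is shown for phi = 0 / phi = 2:

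| Cohort and rate | Table 5 | Negative binomial, 3,000 runs | SAP 10.1 code, 40,000 runs |
|---|---|---|---|
| Cohort 1 at 0.50 | 98.4% / 79.8% | about 85% / 49% | about 85% / 64% |
| Cohort 2 at 0.40 | 97.2% / 79.8% | about 64% / 41% | about 72% / 56% |

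The direction is the same under both models: Table 5 is optimistic. The size depends on which model is final.

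**The case against.** The strongest reply is that the correct statement is already printed three times: in the sentence just before the disputed one, in Protocol 12.4 and in SAP 4. The disputed sentence presents itself as a practical summary, and the SAP does not repeat it. This stands. A reader might infer that the pediatric shortfall was concealed, but the documents do not support that, since the 46.4% is in Table 5 and the 0.40 limit is stated openly. What remains is one sentence that contradicts its neighbours.

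It is also fair to say that 46.4% is the worst tabulated overdispersion and that Cohort 2 has 79.8% at phi = 0. The finding should therefore be given as a range.

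Three further readings are tempting and should not be made:

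- *The missing square root of N invalidates the table.* It does not. Every cell reproduces with sigma/sqrt(N), so the omission is notational. Loss in conversion from PDF cannot be fully excluded, although the same form in both documents makes it unlikely.
- *Describing 0.798 as above 80% is a power error.* The exact figure stands in the same sentence, and Protocol 12.4 and SAP 4 say that the 80% is rounded.
- *A closed-form log-scale calculation gives the planned models' power.* Phi(−ln(mu)/sqrt((1/mu + phi)/N) − 2.326) yields 78% / 45% for Cohort 1 at 0.50 and 61% / 35% for Cohort 2 at 0.40 (phi = 0 / 2). It is a large-sample formula that treats phi as known. For the SAP code it is about 7 to 21 points below the simulation, so these figures should not be quoted as the planned models' power.

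**Conclusion.** The closing sentence of the synopsis is wrong as written for one of the two primary analyses. Against an implied power of about 80%, Cohort 2 at a true rate of 0.50 has 46.4% to 79.8% for phi from 2 to 0, and 63.1% at 0.45 with phi = 2. For Cohort 1 the 0.50 limit agrees with Table 5. These figures rest on the protocol's own assumptions: 20 evaluable children with a year of data each, the stated variance function, and a normal approximation on the mean scale.

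The printed formula needs correcting, but no design figure depends on it. That Table 5 is optimistic for a log-link analysis is a secondary point: the direction is clear, while the amount awaits a settled analysis model. The correction should be made; nothing here calls for a change in design.

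**What to change.** 1. In the synopsis, replace the closing sentence with one to this effect: *adequately powered (about 80%, rounded) for a true rate up to 0.50 in Cohort 1 and up to 0.40 in Cohort 2; at 0.50, Cohort 2 power is 46.4% to 79.8% depending on overdispersion (phi = 2 to 0)*.
2. In Protocol 12.4 and SAP 4, print sigma/sqrt(N) in the power formula. The table values stay as they are.
3. Label Protocol Table 5 and SAP Table 1 as a mean-scale approximation that is optimistic for the planned log-link model, or recompute them by simulating the final analysis model.

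Items 1 and 2 are text corrections. Item 3 costs one sentence, or a short simulation once the model is settled. The stated pediatric power becomes less favourable; enrolment, alpha and the success rule do not change.

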Figure 1.	Safety Evaluation Phase – Randomized Assignment to Scheduling Group	41
Figure 2.	Summary of Stopping Rules	85

List of Abbreviations and Definitions of Terms

Abbreviation	Explanation
ADR	Adverse drug reaction
AE	Adverse event
ALT	Alanine transaminase
AST	Aspartate transaminase
AUC	Area under the curve
AUC _{0-t}	Area under the concentration-time curve over 1 dosing interval
AUC _{0-inf}	Area under the concentration-time curve extrapolated to zero concentration
β2GPI	β2 Glycoprotein I
β2GPI-D1	β2GPI Domain I
B19	Human parvovirus b19
BUN	Blood urea nitrogen
CBC	Complete blood count
CK	Creatinine kinase
CL	Total body clearance
C _{max}	Peak serum concentration
CRA	Clinical research associate
CRO	Clinical research organization
CTA	Clinical trial application
CVID	Common variable immune deficiency
DAT	Direct anti-globulin test
DSMB	Data Safety Monitoring Board
DVT	Deep vein thrombosis
eCRF	Electronic case report form
FDA	Food and Drug Administration
GCP	Good Clinical Practice
HAV	Hepatitis A virus
HBV	Hepatitis B virus
HCV	Hepatitis C virus

HIPAA	Health Insurance Portability and Accountability Act
HIV	Human Immunodeficiency Virus
ICF	Informed Consent Form
ICH	International Conference on Harmonisation
IEC	Independent Ethics Committee
IgA	Immunoglobulin A
IgG	Immunoglobulin G
IGIV	Immune globulin intravenous
IgM	Immunoglobulin M
IGSC	Immune globulin subcutaneous
IMP	Investigational Medicinal Product
IND	Investigational New Drug Application
IRB	Institutional Review Board
IV	Intravenous
LDH	Lactate dehydrogenase
LTSF	Long-term safety follow-up
LTSV	Long-term safety visit
MCH	Mean corpuscular hemoglobin
MCHC	Mean corpuscular hemoglobin concentration
MCV	Mean corpuscular volume
MedDRA	Medical Dictionary for Regulatory Activities
MRT	Mean residence time
NAT	Nucleic acid test
PCR	Polymerase chain reaction
PHI	Protected Health Information
PI	Principal Investigator
PIDD	Primary immunodeficiency diseases
PK	Pharmacokinetics
PP	Per protocol
QA	Quality assurance
QC	Quality control

RBC	Red blood cell
RDW	Red (cell) distribution width
SAE	Serious adverse event
SBI	Serious bacterial infection
SC	Subcutaneous
SD	Standard deviation
SUSAR	Suspected unexpected serious adverse reaction
T _½	Terminal half-life
TCTV	Treatment completion/termination visit
TEE	Thromboembolic event
T _{max}	Time to reach peak serum concentration
TRALI	Transfusion-related acute lung injury
ULN	Upper limit of normal
V _d	Volume of distribution
V _{ss}	Volume of distribution at steady state
WBC	White blood cell
WHO	World Health Organization
XLA	X-linked agammaglobulinemia

1 Introduction

1.1 Background

Primary immunodeficiency diseases (PID) are a class of disorders in which there is an intrinsic defect in the human immune system, in contrast to immune disorders that are secondary to infection, chemotherapy, or some other external agent. PID include a variety of disorders in which the intrinsic immune defect renders patients more susceptible to infections. As a consequence, patients are affected by recurrent protozoal, bacterial, fungal, and viral infections. Untreated PID may be characterized by frequent life-threatening infections.

More than 220 different PID are currently recognized by the World Health Organization (Immune Deficiency Foundation, 2015). Antibody deficiencies, also referred to as B-cell or humoral immunodeficiencies, comprise the largest group of PID (International Union of Immunological Societies, 1999). Common PID include disorders of humoral immunity (affecting B-cell differentiation or antibody production), T-cell defects and combined B- and T-cell defects, phagocytic disorders, and complement deficiencies (Reust, 2013).

ProMetic proposes to include in the study the following three well-defined types of PID, which are associated with humoral immune deficiency and are conventionally treated with immunoglobulin therapy:

- Common variable immunodeficiency (CVID)
- X-linked agammaglobulinemia (XLA)
- Hyper-immunoglobulin M (IgM) syndrome and documented low immunoglobulin G (IgG) levels (< 4.5 mg/mL)

Although PID are often described as rare disorders, remarkably little is known about the true incidence or prevalence in any population, either individually or in the aggregate (Bonilla, 2008; Boyle & Buckley, 2007). There is no universal screening for these defects at birth or at any time during life, anywhere in the world. Overall, there may be as many as 500,000 cases in the United States, of which about 50,000 cases are diagnosed each year (Schroeder, 2001). Some disorders, such as selective IgA deficiency, are quite common and may occur as often as 1 in 400 individuals (Conley, Notarangelo, & Etzioni, 1999; Cunningham-Rundles & Bodian, 1999). Others may be as rare as one individual affected per million. It has been estimated that 40% of cases are diagnosed in the first year of life, with another 40% diagnosed by the age of 5, and another 15% by the age of 16; only 5% of cases are diagnosed in adulthood (Conley & Stiehm, 1996).

The largest registry available on patients with PID is the European Society for Immunodeficiencies (ESID) Registry (Grimbacher & ESID Registry Working Party,

2014). As of June 2014, 19,355 patients were included. Children younger than age 15 years represented two-thirds of the subjects. More than half the patients (57%) had an antibody disorder, and this was also the group with the greatest number of adult patients. Treatment data were available on approximately 14,000 subjects, of whom 6,476 receive immunoglobulin treatment. It is believed that the Registry provides incomplete PIDD prevalence data; for example, the prevalence varies from 2 per 100,000 in Germany to 6 per 100,000 in France. The author believes the apparent difference in prevalence is due to the fact that in France there are designated documenters, financed by local grants, who visit centers to enter patients' data into the Registry.

Boyle and Buckley (Boyle & Buckley, 2007) performed a telephone survey of 10,000 randomly-selected US households and asked an open-ended question: "Has anyone in your household ever been diagnosed with a primary immuno-deficiency disease, such as common variable immunodeficiency, IgA deficiency, IgG subclass deficiency, or any other immunodeficiency?" While admitting the multiple issues associated with this survey, the authors estimated a prevalence of diagnosed PIDD at 1 in 1,200 persons. The specific diagnoses recorded included common variable immunodeficiency, IgA deficiency, IgG subclass deficiency, X-linked agammaglobulinemia, severe combined immunodeficiency, and chronic granulomatous disease.

Joshi et al (Joshi, Iyer, Hagan, St Sauver, & Boyce, 2009) examined trends in the incidence of primary immunodeficiency over 3 decades (1976-2006) in Olmsted County, Minnesota, using 27 ICD-9 codes. This study therefore also included multiple types of primary immunodeficiency. According to this population-based historical cohort study, incidence rates did not differ by sex, but showed an increasing temporal trend in rates over the past 31 years. They found the overall incidence to be 4.6 per 100,000 person-years, with the incidence increasing with time to reach 10.3 per 100,000 persons in the final 5 years of the survey (2001-6). At all periods, the highest incidence of these disorders was in the age group 0-5 years. Overall B-cell defects represented 78% of the population and combined B- and T-cell defects another 10.5%. Among the B-cell defects, IgA deficiency was the most common, accounting for 30% of cases, followed by IgG subclass (IgG2, IgG3, and IgG4) deficiency (26%), and hypogammaglobulinemia (including IgG1 subclass deficiency) (23%). Common variable immunodeficiency was diagnosed in 15% of the cases.

Infections with encapsulated bacteria such as *Haemophilus influenzae* and *Streptococcus pneumoniae* are the most common presenting features of the antibody deficiency syndromes. Other common infectious presenting features include respiratory tract infections (including sinusitis), gastrointestinal infections, meningitis, septic arthritis, and osteomyelitis. Infections often respond to standard treatment, but recur once therapy has been finished. Prolonged and recurrent infection can have significant consequences: in

children poor growth and developmental delay, often as a result of end-organ damage in the respiratory tract. A positive family is of course a strong indicator that a congenital humoral immune deficiency may be present (Wood, 2009).

